# 4.0 Feasibility & Acceptability

# **Primary Objective:**

We estimate based on analyses completed in Phase 1 that approximately 70% of people incarcerated at the two participating institutions meet eligibility criteria. We plan to meet and discuss the study with every eligible individual, as described below, and anticipate that approximately 70% of eligible individuals will agree to participate. Taking this into consideration, we assume 50% of all people who are being released from the institutions will enroll in the study.

We will strive to enroll the 220 participants in the two-year study period or about 9 people per month. We will be enrolling men from Oakhill Correctional Institute (OCI) and women from Wisconsin Women's Correctional System (WWCS).

Due to high volume of potentially eligible individuals, and feasibility of resources for the Nurse Case Manager, potential participants who have anticipated releases to Dane or Milwaukee County will be prioritized in recruitment.

Participants will be considered enrolled after signing the consent form. Active participation in the study will continue until the end-of-study assessment, which will be scheduled to occur 3 months after the date of release from prison. Participants may voluntarily withdraw from the study at any time.

We anticipate that the recruitment goals will be feasible to achieve, based on the annual number of individuals released from the two participating institutions, as shown below.

E	Eligibility				
	Oakhill	REECC	Total		
Total Yearly Average Releases (2019-2022)	316	327	643		
Total Released to Dane and Milwaukee Counties	112	65	177		
Total Released to Rock, Racine, Kenosha, and Waukesha Counties	62	64	126		
Assumed enrollment of eligible individuals (50%)	87	64	151		
Monthly Enrollment Possible	7	5	12		
Total Recruitment Possible (24 months)	168	120	288		

**Secondary Objective:** Preliminary assessment of effectiveness

We will conduct a descriptive analysis of concurrent trends in outpatient health care use among formerly incarcerated adults, focusing on those with a history of a substance use disorder, HCV or HIV. Each year, approximately 9,000 individuals >=18 years are released from Wisconsin state correctional facilities. Based on our prior work, we expect that 70% of these individuals will have one or more of these three conditions. Thus, we expect the population-based analysis will include approximately 20,000 individuals who were released between 1/1/2020-12/31/2023.

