# **Secondary Objective:**

People that meet the following criteria will be included in the sample for our population-based analysis:

- Adults 18 years of age or older,
- Enrolled in Medicaid within one-month of release,
- Has a history of one or more of the following: current HIV infection, current or past HCV infection, identified need for substance use related services based on COMPAS assessment.

We will use several data sources to determine if individuals meet the inclusion criteria (see "Aim 3 Secondary Objective Data.docx"): Wisconsin DOC administrative, COMPAS, and prescription medication data; Wisconsin Medicaid enrollment data; WEDSS surveillance data; and the Wisconsin State Lab of Hygiene.

5.5 Describe the criteria that define who will be excluded from your final study sample.

After application of the inclusion criteria, there are no additional exclusion criteria.

5.6 If any specific population (e.g., racial/ethnic group, sex or gender) will be targeted or excluded, describe this and provide justification.

No specific racial/ethnic group will be targeted.

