# 20.0 Study Analysis

20.1 Statistical Hypotheses: State the formal and testable null and alternative hypotheses for primary and key secondary endpoints, specifying the type of comparison (e.g., superiority, equivalence or non-inferiority, dose response) and time period for which each endpoint will be analyzed.

**Primary Objective:** The main hypothesis to be tested in this pilot study is that the CJC-TraC protocol is feasible and acceptable to WIDOC staff and incarcerated patients.

**Secondary Objective:** The secondary objective is descriptive and not hypothesis driven. The objective is to describe secular trends in health care use among the population from which CJC-TraC participants were recruited. These trends provide a counterfactual regarding what we observe in the absence of the intervention.

Page 31 of 37 Revised: February 16, 2023

20.2 Sample Size Justification: Include number of participants to recruit, screen, and enroll to have adequate power to test the key hypotheses for the study. Include anticipated impact of dropout/withdrawal/cross-over rates, missing data, etc. on study power. Provide all information needed to validate your calculations.

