We will implement descriptive analyses to achieve the following objectives: a) to characterize and compare the equivalence of sample characteristics and outcomes across study years; b) to describe, and test for change over time in unadjusted study outcomes; and c) to quantify the association between study outcomes and factors that may influence those outcomes including beneficiary characteristics. We will use bivariate statistical tests (e.g., t-test, chi-square test) to determine the equivalence of unadjusted characteristics and outcomes over time, and regression methods to estimate changes over time in study outcomes, controlling for individual and areas-level characteristics. For binary outcomes, we will implement logistic regression. For count outcomes, we will implement Poisson regression.

20.5 Planned Interim Analysis: Interim efficacy or safety analyses if planned, and include a description for stopping rules for efficacy and stopping rules for safety.

Interim analyses for feasibility and fidelity will be conducted aligned with the Replicating Effective Programs, such as logging the intensity and frequency of time spent by the Nurse Case Manager on participants, as well as analyses to identify statistically significant barriers to accessing care after release.

20.6 Handling of Missing Data: Describe how missing data will be handled, e.g., type of imputation technique, if any, and provide justification. (Most methods for handling missing data assume that the data are missing at random, which may not be a valid assumption.) WIDOCument reasons for missing data and evaluate the impact of missing data using sensitivity analysis. (If

Page 32 of 37 Revised: February 16, 2023

the missing data are extensive, model-based approaches will estimate their effects under various assumptions regarding missingness.)

Missing data will be considered based on the extent and intensity of the missingness. Steps have been implemented to reduce missingness such as researcher administered surveys, and so we anticipate that missing data will occur randomly. If missing data is extensive, approaches to mitigate the effect of the missing data will be used to generate a functional final model.

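### Section 20.4 uses difference tests with no margin to establish equivalence across release years, which they cannot do (minor; secondary descriptive analysis)

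*Combined protocol and SAP*

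**What the plan says.** Section 20.4 gives three aims for the descriptive analysis of the population cohort. The first is "to characterize and compare the equivalence of sample characteristics and outcomes across study years". The second is to describe, and test for change in, the unadjusted outcomes over time. The third is to relate outcomes to possible explanatory factors. The method for the unadjusted comparison follows: bivariate tests, with the t-test and the chi-square test as examples, are to be used "to determine the equivalence of unadjusted characteristics and outcomes over time". The same sentence adds regression models that estimate change over time with adjustment for individual and area-level characteristics, logistic for binary outcomes and Poisson for counts.

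No equivalence margin, confidence-interval rule, pair of one-sided tests or standardised-difference threshold appears in Section 20.4 or elsewhere. Section 20.1 states: "The secondary objective is descriptive and not hypothesis driven". Sections 13.1 and 20.1 nevertheless say that the population trends supply the counterfactual for this single-group pilot. On size, Section 4.0 says that "we expect the population-based analysis will include approximately 20,000 individuals who were released between 1/1/2020-12/31/2023".

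**The concern.** The named tests have a null hypothesis of no difference. Failing to reject it can mean that years are alike or that the data are too few to tell. Rejecting it can mean an important difference or a trivial one measured precisely. Neither result supports a statement about equivalence unless someone has said how large a difference would still count as equivalent.

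Equivalence appears twice in Section 20.4, and the first aim keeps it apart from testing for change, which is the second. It is therefore hard to dismiss as one stray word. What is at stake is how the report describes the comparability of release years from January 2020 to December 2023. Readers will use those yearly trends as background when they judge whether CJC-TraC participants used more outpatient care than would otherwise be expected. A p-value presented as an equivalence verdict would tell them mostly about the number of people per year.

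**Working it through.** **Cohort size, the plan's own figure.** Section 4.0 gives these inputs: "Each year, approximately 9,000 individuals >=18 years are released from Wisconsin state correctional facilities", and "we expect that 70% of these individuals will have one or more of these three conditions". Over four release years, 9,000 × 0.70 × 4 = 25,200, against the stated 20,000. Section 5.4 adds a further criterion: "Enrolled in Medicaid within one-month of release". The share who meet it is not given. A share of 20,000 / 25,200 = 79% would close the gap, so this is not treated as an error. Both sizes are carried below.

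**Assumptions.**
- An even split across years: 20,000 / 4 = 5,000 per year, or 25,200 / 4 = 6,300.
- Two-sided 5% tests, since no level is stated.
- A proportion of p = 0.34, the 30-day outpatient visit rate in Section 1.2. It is illustrative only. The secondary endpoints in Section 2.2 are the number of visits within 3 months and the days to the first visit.

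**Smallest observed gap between two years that is significant.** The formula is 1.96 × √(2p(1−p)/n). The standardised difference divides this by √(p(1−p)) = √0.2244 = 0.474.

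| People per year | Smallest significant gap | Standardised difference |
|---|---|---|
| 6,300 | 1.96 × √(0.4488/6,300) = 1.7 points | 0.03 |
| 5,000 | 1.96 × √(0.4488/5,000) = 1.9 points | 0.04 |
| 1,000 | 1.96 × √(0.4488/1,000) = 4.2 points | 0.09 |
| 500 | 1.96 × √(0.4488/500) = 5.9 points | 0.12 |
| 100 | 1.96 × √(0.4488/100) = 13.1 points | 0.28 |

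The last three rows are hypothetical strata. The plan names none. They show only that the dividing line follows sample size.

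**How often years would be called different.** With 5,000 per year, the chance of significance is 5% if two years are truly equal, about 18% for a true 1-point gap, 55% for 2 points and 88% for 3 points. With 500 per year, a true 2-point gap is significant about 10% of the time. The same true gap thus tends to opposite labels at different sizes.

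**One result read both ways.** At 5,000 per year the standard error is √(0.4488/5,000) = 0.95 points. An observed gap of 1.9 points has a 95% confidence interval of 1.9 ± 1.86, about 0.0 to 3.8 points. The difference test calls this significant. Under an assumed margin of ±5 points the same result supports equivalence, and under ±3 points it does not. Only a stated margin settles it.

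**Whether a margin rule is workable.** Require the 95% interval to lie inside ±m. If the years are truly equal, the probability of showing equivalence is 2Φ(m/SE − 1.96) − 1, or zero where that is negative. With SE = 0.947 points:
- m = 2: 2Φ(0.15) − 1 = 12%
- m = 3: 2Φ(1.21) − 1 = 77%
- m = 5: 2Φ(3.32) − 1 = over 99%

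With the 90% interval that corresponds to two one-sided 5% tests, the figures are 36%, 87% and over 99%. The margins are assumptions, as the documents give none. The planned data can support a claim at about 3 points or wider, but not at 2.

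**The case against.** The strongest reply is that equivalence is loose wording for comparison. The first aim is to characterise and compare, the tests are given only as examples, and they are suitable for the second aim of testing for change. Regression estimates of change are already planned. The objective is to describe secular trends, and Section 2.1 compares participants with contemporaneous rates, so years need not be equivalent for the trends to be useful. Much of this stands, and it is why the point is minor. It does not repair the sentence: both named examples are difference tests, they are said to determine equivalence, and the regressions address outcomes rather than the balance of characteristics across years.

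Three stronger readings are tempting, and the documents do not support them.

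- **That this check decides whether the population trend may serve as the counterfactual.** Sections 13.1 and 20.1 give the trends that role without condition. Section 20.4 attaches no action to any test result.
- **That very different years will pass as equivalent in small subgroups.** Section 20.4 specifies no year-by-year subgroup tests. In the full cohort, at 5,000 per year, a non-significant gap is below 1.9 points, so its upper 95% limit is below about 1.86 + 1.86 = 3.7 points. That is fairly informative evidence of similarity.
- **That comparable years will regularly fail in the full cohort.** Truly equal years would be flagged 5% of the time and years 1 point apart about 18%, so this is a possibility and not the expected result.

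**Conclusion.** The point holds in a limited form. The tests named in Section 20.4 cannot establish equivalence across release years, because they test for a difference and no margin is stated. In the planned cohort the more likely fault is a small difference labelled as non-equivalence: about 1.9 points (standardised difference 0.04) is enough at 5,000 per year, or 1.7 points at 6,300. In any smaller stratum that the team chose to examine, a non-significant result would not show equivalence.

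These figures rest on an even split across years, two-sided 5% tests and the Phase 1 rate of 34%. The logical point rests on none of them.

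Severity is minor. The yearly trends inform how the pilot's outpatient-visit results are read, but the analysis is secondary and descriptive. No primary feasibility or acceptability endpoint, and no sample-size choice, depends on it.

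**What to change.** In Section 20.4:

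1. Replace the wording about determining equivalence with 'compare', and align the first aim with it.
2. Report standardised differences between release years for characteristics.
3. Report year-to-year differences with 95% confidence intervals for unadjusted outcomes.
4. If equivalence is to be claimed for any outcome, state a margin beforehand and claim it only when the interval lies wholly inside that margin. The team should choose the margin on substantive grounds, knowing that about 5,000 people per year will rarely support one as tight as 2 points.
5. Keep the planned logistic and Poisson regressions.

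The cost is a wording change, a few lines of analysis code and slightly more reporting. No new data are needed and nothing changes for participants.

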- The proportion of DOC staff who rated the intervention acceptable, useful, or appropriate, collected by DOC staff survey.

The referred to questions assess attitudes regarding appropriateness and acceptability of the CJC-TraC intervention, and do not include questions about respondents themselves. Pilot intervention participants and WIDOC staff involved with the CJC-TraC pilot program at Wisconsin Women's Correctional System (WWCS) and Oakhill Correctional Institutions will be asked questions to capture perceptions about the intervention itself at the conclusion of the pilot intervention. WIDOC staff are not considered research subjects as a result of being asked these questions as they are not being asked to share data about themselves, but rather professionally assess the intervention. In addition to assessing the acceptability and appropriateness of CJC-TraC, pilot intervention participants provide additional identifiable and personal data throughout the lifespan of the study and are therefore considered research participants.

Secondary Endpoints: Effectiveness

- The number of non-emergency outpatient visits observed within 3-months following release.
- The number days until the first non-emergency outpatient visit following release.

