The proposed sample size was chosen by considering what would be an appropriate case load and frequency of client interactions for the Nurse Case Manager. This level was informed by focus group data collected in Phase 1 and input from collaborators, and eligible participants at the two correctional institutions where the study will occur. Publicly available data from the Department of Corrections indicates that Oakhill Correctional has approximately 316 annual releases while Robert E. Ellsworth Correctional Center (REECC), a facility in the Wisconsin Women's Correctional System (WWCS), has approximately 327, for a total of 643 annual releases at the two study sites. There are 112 and 65 people released to Dane and Milwaukee counties annually at Oakhill and REECC respectively, for a total of 177. These counties will be prioritized for recruitment. An additional 126 individuals released annually to Rock, Waukesha, Racine, and Kenosha counties, 62 from Oakhill and 64 from REECC. These counties can be adequately serviced by the NCM at this time, and the number of serviceable counties will increase throughout the intervention. Assuming that 50% of people incarcerated at the two facilities and releasing to a serviceable county will be eligible and enroll in the study, we would expect a total of 168 participants at Oakhill Correctional Institution and 120 at REECC over the 24-month study period, for a total of 288 total participants. Our recruitment goal is 220 individuals.

20.3 Participant Population(s) for Analysis: Identify and describe the analysis datasets (e.g., which participants/populations will be included in each).

The dataset construction begins with all individuals released from a WI state correctional facility between 1/2020-12/2023. From this universe of individuals, we will apply the sample criteria noted in 5.4 to generate the analytic dataset: adults who have a history of, or living with, SUD, HCV or HIV and enroll in Medicaid within the month of release.

20.4 Statistical Methods: Summarize the overall statistical approach to the analysis of the study data.

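### Days to first outpatient visit has no window and no rule for people without a visit, and the Poisson model for visit counts has no stated allowance for overdispersion

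*Combined protocol and SAP*

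**What the plan says.** Section 2.2 sets two effectiveness endpoints: "The number of non-emergency outpatient visits observed within 3-months following release" and "The number days until the first non-emergency outpatient visit following release". The first has a three-month window; the second has none.

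Section 20.4 holds the statistical methods. One of its aims is "to describe, and test for change over time in unadjusted study outcomes". For unadjusted comparisons it begins "We will use bivariate statistical tests (e.g., t-test, chi-square test", so those tests are examples. For adjusted change over time it relies on regression: "For binary outcomes, we will implement logistic regression. For count outcomes, we will implement Poisson regression". Section 20.6, on missing data, says "we anticipate that missing data will occur randomly" and rests this on surveys being administered by researchers.

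No section mentions censoring, a time-to-event method, a value for people with no visit, person-time, overdispersion or robust variance. Section 12.1 says that Medicaid data will be collected for one year after release. Section 20.1 limits the ambition: "The secondary objective is descriptive and not hypothesis driven".

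**The concern.** A person who never has a visit has no number of days to the first one. A t-test on days needs a number for everyone, and so does a Poisson model that treats days as a count. The analyst must then leave non-visitors out, assign them a value, or move to a method that the plan does not name. As written, that choice is made after the data are seen.

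It matters because the endpoint will be used. Section 20.4 plans tests and adjusted estimates of change across study years. Section 2.1 expects participants to use outpatient care at a higher rate than comparable people, Section 13.1 reads effectiveness from departures from the population trend, and Section 2.1 says that the pilot data will inform later trials.

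For visit counts the question is narrower. Poisson point estimates remain usable if visits cluster in a few heavy users, but the model-based standard errors are then too small.

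**Working it through.** The plan states no power, variance or error-rate figure for these two endpoints, so there is nothing of its own to reproduce. The steps below start from its one relevant figure.

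**Input.** About 34% have at least one outpatient visit within 30 days (Section 1.2, a Phase 1 cohort enrolled in Medicaid at release). So S(30) = 0.66, where S(t) is the share with no visit by day t. The daily hazard over days 0 to 30, taken as constant, is λ = −ln(0.66)/30 = 0.01385, and 1/λ = 72.20 days.

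**Step 1: share with no visit by day 90.** The documents do not give the hazard after day 30, so three assumed shapes are used:
- constant hazard: 0.66³ = 0.287
- hazard halves after day 30: 0.66 × 0.66 = 0.436
- no first visits after day 30: 0.66

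Of 220 participants, the two ends are 220 × 0.287 ≈ 63 and 220 × 0.66 ≈ 145 people.

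**Step 2: two summaries of days.** The 90-day restricted mean (RM) keeps everyone and counts non-visitors as 90 days. The visitors-only mean is (RM − 90·S(90)) / (1 − S(90)).
- Constant hazard: RM = (1 − 0.2875) × 72.20 = 51.4; visitors only = (51.44 − 25.87)/0.7125 = 35.9.
- No first visits after day 30: RM = 0.34 × 72.20 + 60 × 0.66 = 24.5 + 39.6 = 64.1; visitors only = (64.15 − 59.40)/0.34 = 14.0.

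| Assumed shape after day 30 | No visit by day 90 | Visitors-only mean (days) | Restricted mean (days) |
|---|---|---|---|
| Constant hazard | 29% | 35.9 | 51.4 |
| Hazard halves | 44% | 31.4 | 57.0 |
| No first visits | 66% | 14.0 | 64.1 |

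The two summaries rank these patterns in opposite order.

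**Step 3: a proportional difference.** Suppose the hazard is 1.5 times higher throughout. Then S(90) = 0.66^4.5 = 0.154, the restricted mean is 40.7 and the visitors-only mean is 31.7. The gain is 51.4 − 40.7 = 10.7 days on the first summary and 35.9 − 31.7 = 4.2 days on the second: the same direction, but much weaker. In a simulation of 220 people against an assumed 2,200 comparators (1,000 data sets, 5% level, constant hazard, censoring at day 90), a visitors-only t-test rejected in 18% of data sets at hazard ratio 1.25, against 79% for a log-rank test. At hazard ratio 1 both stayed near 5% (4.4% and 4.8%), so under these assumptions the loss is in sensitivity, not in false positives.

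**Step 4: counts.** Let φ be the variance-to-mean ratio, which the documents do not give. Model-based Poisson standard errors are too small by √φ, and a nominal 95% interval covers 2Φ(1.96/√φ) − 1.

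| Assumed φ | √φ | Coverage |
|---|---|---|
| 1 | 1.00 | 95% |
| 1.5 | 1.22 | 89% |
| 2 | 1.41 | 83% |
| 3 | 1.73 | 74% |
| 5 | 2.24 | 62% |

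**The case against.** The best defence is that the plan is open rather than wrong. Its tests are examples, its reference to regression is general, and Section 20.4 is a summary. Logistic regression is named, and a visit by day 30 (the Phase 1 measure in Section 1.2 and the program goal in Section 13.1) would keep everyone. Logistic or Poisson regression can even be set up as a survival model, given person-period data or person-time. This stands in part: nothing rules out a suitable analysis. But a visit by day 30 is not the listed endpoint, and the plan gives neither the set-up nor the censoring day that a survival version needs. Section 20.6 does not fill the gap, because having no visit is an observed result and not a missing survey answer.

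The objective is also secondary and described as not hypothesis driven. That lowers the stakes, but a descriptive summary of days still needs a rule for non-visitors. The choice of variance estimator can fairly be called coding detail; that part of the point is the weaker one.

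A reader might infer more than the documents support:
- **That non-visitors will be dropped.** The plan neither proposes nor excludes this.
- **That a visitors-only mean would reverse a comparison.** The reversal in Step 2 needs different hazard shapes after day 30, one of them extreme. Under a proportional difference the effect is weakened, not reversed.
- **That Poisson regression is the wrong model, or that counts are overdispersed.** It is a legitimate model, and every ratio above 1 here is an assumption.
- **That unequal Medicaid time biases participants against the population.** For the cohort, Section 20.3 takes people who "enroll in Medicaid within the month of release", Section 6.3 speaks of at least one month of enrollment, and Section 23.1 expects some re-incarceration. But Section 5.1 asks participants to be willing to enroll before release, Section 11.1 makes enrollment a case-manager task, and Section 8.1 seeks clinic records with visit dates. No late-entry or re-incarceration rate is given, so neither size nor direction can be stated.

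**Conclusion.** The point holds, chiefly for days to first visit. The omission is certain: there is no window, and no named method as described accommodates people without a visit. Its effect depends on assumptions. The 29% to 66% range rests on the Phase 1 figure for any outpatient visit, on the assumed hazard after day 30 and on a 90-day window; with the full year of Medicaid data the share without a visit could only be the same or smaller. Within that range, leaving non-visitors out would weaken or distort differences between years, or between participants and the population trend.

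For counts, the point is only that the stated model needs an interval that remains valid if the variance exceeds the mean. This should be fixed, but it does not touch the feasibility and acceptability endpoints, which are primary.

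**What to change.** In Section 20.4:
- **Days to first visit.** Analyse it as time to event from release and keep everyone with no visit. Censor at a stated day; day 90 would match the three-month count endpoint, although the Medicaid data run longer. Report cumulative incidence at days 30 and 90. Use a Cox model for the adjusted change over time that is already planned, cause-specific if re-incarceration or death is treated as a competing event and the dates are available.
- **Visit counts.** Keep Poisson regression with robust standard errors, or use negative binomial regression. If variance equals the mean, this leaves the conclusions essentially as they were.
- **Optional sensitivity analysis.** Add the log of observable Medicaid-enrolled days in the community as an offset to the count model, and report the share enrolled after release.

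The cost is a few sentences, standard code and a little more analysis work. Count intervals become somewhat wider if there is overdispersion. Medicaid enrollment data are already a listed source (Section 5.4); the availability of re-incarceration and death dates must be confirmed first.
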